### 5.2.1.2 Withdrawal from follow-up period

Following completion of the EOT visit, patients who discontinue study treatment due to PD will enter the Safety follow-up period, and patients who discontinue study treatment for reasons other than PD will enter Active follow-up period (which also serves as a Safety follow-up).

During the Survival follow-up period all patients will be contacted every 3 months to determine survival status (up to 7 years after the last patient started study treatment).

Reasons for not performing the Safety follow-up or discontinuation of the Survival follow-up include the following:

- Death
- Objection to follow-up data collection
- Lost to follow-up

### 5.2.2 Replacement

Patients will not be replaced.

### 5.3 Patient identification

At Screening upon signing the ICF, each patient will be assigned a unique patient identification number (PID) by the IVRS/IWRS for unambiguous identification. The PID will be constructed as follows:

- a. Digits 1 to 2: Unique country code
- b. Digits 3 to 5: Center code (unique within each country)
- c. Digits 6 to 9: Unique patient code (unique within each center)

Within the unique patient code, the first digit (digit 6) represents the study a patient is participating in.

Patients participating in study 17067 (this study) have a "7" as the 6th digit. As an example, PIDs in this study have the structure "aabbb7ccc".

Once allocated, the patient's PID number will identify the patient throughout the study and will be entered into the Site Enrollment Log and in the eCRF.

09 FEB 2023 Page: 41 of 151

### 6. Treatments

### 6.1 Treatments to be administered

The study treatment (=study drugs) will comprise the following:

- The combination of the test drug copanlisib (BAY 80-6946) and rituximab, to be administered as combination therapy. Copanlisib will be administered before rituximab.
- The combination of placebo and rituximab, to be administered as combination therapy. Placebo will be administered before rituximab.

For the dosage and administration please see Section 6.4.

### 6.2 Identity of investigational medicinal products

All study drugs will be labeled according to the requirements of local law and legislation. The label text will be approved according to the sponsor's agreed procedures, and a copy of the labels will be made available to the study site upon request.

For all study drugs, a system of numbering in accordance with all requirements of Good Manufacturing Practice (GMP) will be used, ensuring that each dose of study drug can be traced back to the respective bulk batch of the ingredients. Lists linking all numbering levels will be maintained by the sponsor's clinical supplies Quality Assurance group.

A complete record of batch numbers and expiry dates of all study treatment as well as the labels will be maintained in the sponsor's study file.

Only patients enrolled in the study may receive study treatment and only authorized site staff may prepare, supply, or administer study treatment.

An approved representative at the site will ensure that all received study drugs are stored in a secured environmentally controlled and monitored (manual or automated) area in accordance with the labeled storage conditions with access limited to the investigator and authorized site staff.

The investigator or approved representative at the site is responsible for study intervention accountability, reconciliation, and record maintenance (i.e., receipt, reconciliation, and final disposition records).

Further guidance and information for the final disposition of unused study interventions are provided in the Pharmacy Manual.

### Copanlisib (test drug)

Copanlisib is supplied as lyophilized preparation in a 6 mL injection vial. The total amount of BAY 80-6946 per vial is 60 mg. The solution for IV infusions is obtained after reconstitution of the lyophilisate with normal saline solution.

Please refer to the Pharmacy Manual for detailed instructions for the reconstitution of the lyophilisate and for further dilution of the reconstituted solution.

Please refer to IB for copanlisib for more details regarding drug properties and formulation.

### Placebo for copanlisib

Placebo is supplied as lyophilized preparation in a 6 mL injection vial. Placebo treatment will follow a dosing scheme to match the active drug product. Accordingly, the developed placebo

09 FEB 2023 Page: 42 of 151

lyophilisate is equivalent to the 60 mg copanlisib formulation, with regard to the composition of excipients and the instructions for reconstitution and dose preparation.

Reconstitution, dilution and storage of placebo preparation should be performed according to same instructions as for copanlisib.

For the guidance on preserving the blinding during handling of the study treatment, refer to Section 6.5.

#### Rituximab

Rituximab will be sourced centrally or locally by the sponsor depending on the local law and requirements. For full details on rituximab and instructions for dilution, please refer to the current prescribing information / Summary of Product Characteristics (SmPC).

### 6.3 Treatment assignment

At the end of the screening period, eligible patients will be randomly assigned in a 2:1 ratio to the two double-blinded treatment arms: copanlisib + rituximab or placebo + rituximab, respectively.

Treatment will be assigned based on information obtained from IVRS/IWRS.

IVRS/IWRS will stratify patients according to four factors based on baseline characteristics:

- NHL histology
  - FL histology
  - o Other iNHL histology (SLL, MZL, LPL/WM)
- Entry criterion:
  - o progression-free and treatment-free interval of  $\geq 12$  months after completion of the last rituximab-containing treatment
  - o considered unwilling/unfit to receive chemotherapy for age or comorbidities (see inclusion criterion 13 for further details)

If the patient fulfills both entry criteria, please select the criterion "considered unwilling/unfit to receive chemotherapy for age or comorbidities".

- Presence of bulky disease (as defined by the presence of a nodal or extranodal mass ≥ 7 cm in the longest diameter, with the exception of spleen):
  - o yes
  - $\circ$  no
- Previous treatment with PI3K inhibitors
  - o yes
  - o no

Resulting from the combination of these 4 stratification factors, patients will be randomized into 16 different strata. The randomization must be performed up to maximum 72 h before the first dose of study treatment.

The IVRS/IWRS procedure is described in detail in a separate IVRS/IWRS instruction manual.

Due to the potential of bias or unblinding, the size of randomization blocks within the randomization list must not be disclosed to blinded study individuals.

09 FEB 2023 Page: 43 of 151

During the course of the study, the randomization list will be provided to the Statistical Analysis Center for the DMC and its meetings, the Bioanalytics group and the Pharmacokinetic Evaluator in order to perform the PK analysis.

### 6.4 Dosage and administration

### Copanlisib and placebo

Cycle 1 Day 1

Copanlisib and placebo for copanlisib formulations are administered before rituximab, in a normal saline solution, intravenously, over approximately 1 h. See Pharmacy Manual for additional details. No intravenous glucose preparations should be administered on the days of infusion

Dosing is weekly for the first 3 weeks of a 28-day cycle (on Days 1, 8, and 15), followed by a 1-week break (i.e., no infusion on Day 22).

The requirements for fasting state and pre-dose glucose levels are presented in Table 6–1.

 Period
 Fasting ≥ 8 h required before first glucose measurement
 Pre-dose glucose levels (first glucose measurement)

 Cycle 1 Day 1
 Yes a
 ≤125 mg/dL (non-diabetic patients)

 <160 mg/dL (diabetic patients)	<160 mg/dL (fasting)	Subsequent infusions after
 No b
 <200 mg/dL (non-fasting)	Table 6–1 Fasting requirements and pre-dose glucose levels

- Fasting refers to  $a \ge 8$  h fast.
- Non-fasting status includes any caloric intake such as meals and also juice, snacks, and other caloric intake not consistently called a meal.

From Cycle 1 Day 1 onwards, glucose measurements at the site may be done either by laboratory analysis or in capillary blood.

Because of inhibitory effect on PI3K  $\alpha$ -isoform, which is implicated in insulin metabolism, copanlisib infusions could be associated with temporary increase in blood glucose. Addition of meal in close proximity to copanlisib/placebo infusion may exacerbate glucose increase.

On infusion days, a low calorie or low carbohydrate diet is recommended. The timing and content of meal intake and additional glucose testing (if clinically indicated) is managed and monitored by the investigators based on glucose response patterns during prior treatment days. Consultation with diabetologist or endocrinologist is advised.

All glucose measurements done at the site, oral glucose lowering medication and/or insulin administration, if applicable, fasting/non-fasting status and meal intake timing on infusion days will be collected as part of the clinical source documentation.

<sup>a Diabetic patients who take insulin treatment at any cycle visit: Timing and content of meal intake will be managed by the investigator. Consultation with treating physician or diabetologist/endocrinologist is advised.

<sup>b The decision regarding meal timing and fasting can be made by the investigator based on glucose response patterns during prior treatment days.

09 FEB 2023 Page: 44 of 151

### Rituximab

Rituximab will be given IV at 375 mg/m^2 body surface weekly during Cycle 1 (on Days 1, 8, 15 and 22). Although the dose is calculated by the IVRS/IWRS, a minor variation ( $\pm 5\%$ ) of the recommended dose is allowed due to the local standard of care disbursing requirements. However, a +5% variance is only permitted if a new vial is not required. For those patients who are still on treatment after evaluation at the end of Cycle 2 (not in PD), rituximab will be administered once in each of Cycles 3, 5, 7 and 9 (on Day 1). It will be administered taking into account all measures of precaution prescribed by the manufacturer to avoid infusion reactions (rate of infusion, premedication, etc.). Patients will be monitored according to rituximab SmPC.

### **Dosing criteria**

Starting from Cycle 1 Day 8, laboratory tests prior to each infusion may be performed either the day before or on the planned date of infusion, with the exception of glucose, which must be performed on the day of copanlisib/placebo infusion. All laboratory results must be assessed by the investigator and/or appropriate site personnel prior to administration of the planned dose.

On Day 1 of each subsequent cycle, the dose of study treatment will be given only if the criteria described in Table 6–2 are met.

09 FEB 2023 Page: 45 of 151

Table 6-2 Laboratory test criteria for Day 1 dose of subsequent cycles

Laboratory Test	Criteria for Day 1 dose (Cycle 2 and higher)
Glucose	< 160 mg/dL (fasting) or < 200 mg/dL (non-fasting)
Hemoglobin	≥ 8 g/dL a
ANC	≥ 1,000/mm³. For patients with confirmed lymphomatous bone marrow infiltration at screening and ANC ≥ 750/mm³ - < 1000/mm³: ANC ≥ 750/mm³. b
Platelets	≥ 50,000/mm 
ALT	≤ 5 X ULN
AST	≤ 5 X ULN
Total bilirubin	≤ 3 X ULN
GFR (MDRD)	≥ 30 mL/min/1.73 m 

ALT = alanine aminotransferase, ANC = absolute neutrophil count, AST = aspartate aminotransferase, GFR = glomerular filtration rate, MDRD = modification of diet in renal disease, ULN = upper limit of normal

- If ANC ≥ 1000/mm³ during screening, the limit of ANC ≥ 1000/mm³ should be applied during the study.
- If after screening the ANC raises to levels above 1000/mm³, it is recommended to confirm the result of the test within 1 day. Unconfirmed single assessment or confirmed double assessment of ANC > 1000/mm³ warrants ANC ≥ 1000/mm³ to receive further doses of study drugs for this patient for the remainder of the study.

A blood count will be performed and assessed prior to the subsequent doses in each cycle of copanlisib/placebo on Days 8 and 15. The study drug will not be administered if, on the day of scheduled dosing, any of the following criteria is met:

- CTCAE Grade 4 neutrophil count decreased (ANC < 500/mm^3)
   (G-CSF is mandatory if ANC < 1000/mm^3 and should be administered as per label)
- CTCAE Grade ≥ 3 platelets count decreased (platelets < 50,000/mm^3)
- CTCAE Grade  $\geq$  3 anemia (hemoglobin  $\leq$  8 g/dL), see footnote a in Table 6–2

Doses scheduled for Days 8 and 15 may be delayed by up to 2 days. A delay of more than 2 days will be considered a missed dose. Missed doses will not be replaced. The minimum interval needed between two infusions of copanlisib/placebo is 5 days.

<sup>a If hemoglobin is < 8 g/dL but ≥ 6 g/dL on the day of planned study drug administration it is permissible to give the study drug dose as scheduled and transfuse within 48 h after the dose, if the patient is hemodynamically stable and in opinion of investigator benefits outweigh risks. Rationale and treatment should be recorded in source document and eCRF.

<sup>b For patients with lymphomatous bone marrow infiltration:

09 FEB 2023 Page: 46 of 151

### **6.4.1** Dose modification

Dose modifications due to toxicities described below apply to copanlisib and placebo for copanlisib ("dummy dose modification"). There will be no dose reduction of rituximab. If severe (life-threatening) reaction to rituximab infusion occurs despite supportive treatment patients should be withdrawn from the study treatment. Patients must have received at least 4 complete rituximab infusions until Cycle 3 Day 1 (included) to continue the treatment with single agent copanlisib/placebo.

It is recognized that attribution of causality of any AE to the test drug specifically may be difficult. However, certain toxicities were seen only in relation to copanlisib in Phase I and II trials: e.g., transient increases in glucose and blood pressure. Based on this knowledge the investigator may decide on the necessary dose modifications.

Dose modifications and treatment interruptions must be done according to the guidelines in Section 6.4.1.1 and 6.4.1.2. The investigator may judge a more conservative dose modification appropriate. If therefore these guidelines are not followed, the rationale for other measures is to be documented in detail in patient's medical record. Deviations from the guidelines must be discussed with the sponsor.

The dose modification levels of copanlisib and placebo are outlined in Table 6–3:

Table 6-3 Dose levels of copanlisib and placebo

Dose level 1 (starting dose):	60 mg of copanlisib or placebo
Dose level -1:	45 mg of copanlisib or placebo
Dose level -2:	30 mg of copanlisib or placebo

After having fully recovered from toxicity and in the absence of any criteria for further dose reduction or study drug discontinuation, re-escalation from dose level -2 to dose level -1, or from dose level -1 to dose level 1 will be allowed at the investigator's discretion, with the exception of non-infectious pneumonitis (NIP).

Patients who do not tolerate the copanlisib/placebo dose of 30 mg must discontinue study treatment permanently.

09 FEB 2023 Page: 47 of 151

### 6.4.1.1 Hematological toxicity

Neutropenia and febrile neutropenia are listed in the current version of IB as expected adverse events. If the guidelines given in Table 6–4 are not followed, the rationale for other measures is to be documented in detail in the patient's medical record.

Table 6–4 Dose modification of copanlisib/placebo for hematological toxicity

# CTCAE Grade ≥ 3 thrombocytopenia (platelet < 50,000/mm³)
 Febrile neutropenia or ANC < 500/mm³ a
 INR or PTT CTCAE Grade ≥ 3 with bleeding e CTCAE Grade ≥ 3 anemia (Hb < 8 g/dL)
 Test drug action (for any toxicity) Delay infusion until criteria displayed in Table 6-2 are met. d Patient can be treated at one dose level lower at the investigator's discretion. If more dose reductions are required than allowed per protocol, discontinue copanlisib permanently. The lowest dose level is 30 mg.

ANC = absolute neutrophil count; CTCAE = Common Terminology Criteria of Adverse Events, version 4.03; G-CSF = Granulocyte colony stimulating factor; Hb = hemoglobin; INR = international normalized ratio, PTT = partial thromboplastin time

- a For patients who develop CTCAE Grade ≥ 3 neutropenia, a blood count after 3 days is recommended. For patients with CTCAE Grade 3 neutropenia and no bone marrow infiltration, consider reducing the dose of copanlisib until recovery to Grade 2 and also consider the use of myeloid stimulating factor as long as the patient responds or does not progress. G-CSF is mandatory if ANC < 1000/mm³ and should be administered as per label).
- b After having fully recovered from toxicity and in the absence of any criteria for further dose reduction or study drug discontinuation, re-escalation to dose level -1 or 1 will be allowed at the investigator's discretion.
- c Footnote c deleted by amendment 7.
- d Treatment with transfusion or growth factors is allowed at the investigator's discretion.
- e INR and PTT should have returned to ≤ 1.5 and ≤ 1.5 x ULN, respectively, with no signs of bleeding.

### **6.4.1.2** Non-hematological toxicity

Dose modifications for non-hematologic toxicities except glucose increases, dermatologic toxicity, non-infectious pneumonitis and arterial hypertension are outlined in Table 6–5.

09 FEB 2023 Page: 48 of 151

Table 6–5 Dose modification of copanlisib/placebo for non-hematological toxicity (except glucose increases, dermatologic toxicity, non-infectious pneumonitis and arterial hypertension)

		Test Dru	g Action				
Toxicity a	Occurrence	For current course of therapy	For next course of therapy				
Grade 1-2	Any appearance	No change	No change				
Grade 3 b	1 st appearance	Interruption until Grade ≤ 2	No change				
	2 nd appearance	Interruption until Grade ≤ 2	Decrease by one dose level c				
	3 rd appearance	Interruption until Grade ≤ 2	Decrease by one dose level c				
	4th appearance	Permanent discontinuation	_				
Grade 4	Any appearance	Permanent discontinuation	_				
Toxicity requi	Toxicity requiring delay for > 28 days Permanent discontinuation –						

<sup>a Toxicities according to CTCAE version 4.03

A delay > 28 days in study drug administration due to toxicities will cause permanent discontinuation of study treatment. Except, in case of delays due to reactivation of cytomegalovirus (CMV) where delays could be up to 2 months.

Copanlisib/placebo must be discontinued if the lowest dose level of 30 mg is not tolerated.

After having fully recovered from toxicity and in the absence of any criteria for further dose reduction or study drug discontinuation, re-escalation to dose level -1 or 1 will be allowed at the investigator's discretion.

### **Dermatologic toxicity**

The guidelines for dose modifications in cases of dermatologic toxicity are outlined in Table 6–6. If these guidelines are not followed, the rationale for other measures will be documented in detail in the patient's medical record.

Table 6-6 Dose modification of copanlisib/placebo for dermatologic toxicity

		Study Drug Action	
Toxicity a	Occurrence	For current course of therapy	For next course of therapy
Grade 1	Any appearance	No change	No change
Grade 2 b	1st appearance	Interruption until Grade ≤ 1	No change
	2 nd appearance	Interruption until Grade ≤ 1	Decrease by one dose level c
	3 rd appearance	Interruption until Grade ≤ 1	Decrease by one dose level c
	4 th appearance	Permanent discontinuation	-
Grade 3 b	1st appearance	Interruption until Grade ≤ 1	Decrease by one dose level c
	2 nd appearance	Interruption until Grade ≤ 1	Decrease by one dose level c
	3 rd appearance	Permanent discontinuation	_
Grade 4	1 st appearance	Permanent discontinuation	-

<sup>a Toxicities according to CTCAE version 4.03

The lowest dose level is 30 mg; if a patient is already on the 30 mg dose level study drug and meets criteria for further decrease of dose, study drug will be discontinued permanently.

<sup>b Despite maximum supportive therapy

<sup>c Not applicable for 30 mg dose level (footnote d deleted by amendment 1)

<sup>b Despite maximum supportive therapy

<sup>c Not applicable for 30 mg dose level (footnote d deleted by amendment 1)

09 FEB 2023 Page: 49 of 151

### Non-infectious pneumonitis (NIP)

In the event of suspected NIP of any grade, copanlisib/placebo treatment should be adjusted according to the guidance in Table 6–7.

Table 6–7 Dose adjustment in cases of non-infectious pneumonitis (NIP)

Suspected or confirmed NIP per CTCAE	Action Taken	Re-treatment dose after recovery
Grade 1	No change	NA
Grade 2	Dose interruption until recovery to ≤ Grade 1	Decrease dose to the next lowest dose level a
Grade 2 second re-occurrence	Permanent discontinuation	NA
Grade 3	Permanent discontinuation	NA
Grade 4	Permanent discontinuation	NA

NA = Not applicable; NIP = Non-infectious pneumonitis; CTCAE = Common Terminology Criteria for Adverse Events.

Pneumonitis is to be reported as such only in the event of NIP. The investigator is requested to differentiate between non-infectious pneumonitis (NIP) and infectious pneumonitis (viral, bacterial, fungal), aspiration pneumonitis, or other pneumonitis.

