### 5.2.1.1 Withdrawal of study treatment

Patients *must* be withdrawn from the study treatment for the following reasons:

- At their own request or at the request of their legally acceptable representative. At any time during the study and without giving reasons, a patient may decline to participate further. The patient will not suffer any disadvantage as a result. Patients who withdraw consent from treatment will still participate in the Safety, Active or Survival follow-up unless they object to follow-up data collection (see Section 11.2).
- If, in the investigator's opinion, continuation of the study would be harmful to the patient's well-being.
- Disease progression as defined in the Lugano Classification and, for patients with WM, according to the Owen Criteria.
- Occurrence of unacceptable toxicity.
- CTCAE Grade 4 arterial hypertension.

09 FEB 2023 Page: 39 of 151

- Persistent occurrence of post-infusion blood glucose > 500 mg/dL based on laboratory analysis which occurred at the lowest copanlisib/placebo dose level despite optimal glucose lowering therapy (after at least one cycle of treatment).
   Definition of persistent occurrence is based on repeated post-infusion blood glucose laboratory analysis taken at different time during the whole cycle of treatment.
- CTCAE Grade 4 dermatologic toxicity.
- CTCAE Grade ≥3 (or recurrent Grade 2) non-infectious pneumonitis.
- Drug-induced pancreatitis.
- Development of a malignancy other than indolent B-cell NHL. New malignancy will be reported as an SAE.
- Start of a new anti-cancer regimen.
- The patient does not tolerate copanlisib/placebo dose of 30 mg.
- The patient presents during further testing a positive viral load when initial HBV DNA and/or HCV RNA testing was negative.
- Severe allergic reaction to test drug (such as CTCAE Grade 3 or 4 hypersensitivity reaction).
- Severe (life-threatening) reaction to rituximab infusion despite optimal supportive treatment.
- Patient lost to follow-up.
- Substantial non-compliance with the requirements of the study.
- Delay in test drug administration due to toxicities for > 28 days (a delay of test drug dosing due to reasons other than toxicity is not included in this definition). Except, in case of delays due to reactivation of CMV where delays could be up to 2 months.
- Development of any intercurrent illness or situation which, in the judgment of the investigator, may affect assessments of clinical status and study endpoints to a relevant degree.

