### b) Arterial hypertension

The guidelines for dose modifications of copanlisib/placebo in case of arterial hypertension are given in Table 6–8.

No dose should be given if blood pressure is  $\geq 150/90$  mmHg. Instructions for blood pressure measurement are given in Section 7.5.3.3. Antihypertensive medication may be given to

a: Not applicable for 30 mg dose level. No re-escalation is allowed after the dose reduction.

The lowest dose level is 30 mg; if a patient is already on the 30 mg dose level and cannot tolerate treatment study treatment will be discontinued permanently.

09 FEB 2023 Page: 50 of 151

control the arterial hypertension. Dosing can proceed on the scheduled day if there are at least 2 consecutive measurements <150/90 mmHg. Otherwise dosing must be delayed.

If drug-related arterial hypertension (post-dose blood pressure of CTCAE Grade 3 or  $\geq 160/100$  mmHg) is not manageable with optimal antihypertensive treatment, the dose for the subsequent copanlisib/placebo administrations may be reduced by 1 or 2 dose levels at the investigator's discretion. Guidelines for the treatment of blood pressure increases are given in Section 6.4.2.3. Patients with a hypertension of CTCAE Grade 4 must permanently discontinue the study drug (see Section 5.2.1.1).

Table 6–8 Dose modification of copanlisib/placebo for arterial hypertension

Toxicity (CTCAE)	Study drug action	Recommendation
Pre-dose measurements BP ≥ 150/90 mmHg	No dose should be given until recovery to < 150/90 mmHg.	Consider BP lowering medication. Dosing can proceed on the scheduled day if after at least 2 consecutive measurements BP returns to < 150/90 mmHg. If BP doesn't return to < 150/90 mmHg, delay dosing until next visit.
During infusion: CTCAE hypertension of grade 3 or ≥ 160/100 mmHg	Infusion can be interrupted or slowed down and administration of BP lowering therapy should be initiated.	Infusion may be resumed immediately when BP has returned to < 150/90 mmHg or otherwise skipped.  Subsequent study drug administrations may be reduced by 1 dose level at the investigator's discretion. b

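### Section 5.2.1.1 and Table 6-7 can be read to give different actions for a second Grade 2 episode of non-infectious pneumonitis

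*Protocol*

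**What the plan says.** Section 5.2.1.1 of the protocol lists the reasons for which a patient must come off study treatment. One entry covers NIP of Grade 3 or higher, "or recurrent Grade 2) non-infectious pneumonitis".

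Section 6.4.1.2 deals with NIP separately. It states that "copanlisib/placebo treatment should be adjusted according to the guidance in" Table 6-7. That table has two Grade 2 rows:

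- Plain Grade 2, with no occurrence number: hold the drug until the event has fallen to Grade 1 or less, then "Decrease dose to the next lowest dose level".
- "Grade 2 second re-occurrence": permanent discontinuation.

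Footnote a to the table says that the reduction step does not apply at 30 mg, and adds: "No re-escalation is allowed after the dose reduction". Neither place defines recurrence, and the NIP text in Section 6.4.1.2 does not cross-refer to Section 5.2.1.1.

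The neighbouring tables count episodes explicitly. Table 6-5 (other non-hematological toxicity) runs up to a "4th appearance" row for Grade 3, and Table 6-6 (dermatologic toxicity) starts its count at "1st appearance". Table 6-7 does not use that format.

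**The concern.** A site whose patient has a second Grade 2 episode can find two answers in the current protocol: mandatory withdrawal in Section 5.2.1.1, or interruption and re-treatment one level lower under the unnumbered Grade 2 row of Table 6-7. Section 7.5.1.6 names NIP as the only adverse event of special safety interest and requires immediate notification whether or not it is serious.

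Which patients are recorded as withdrawn for NIP, what action is recorded for the event, and whether a case is treated as a protocol deviation could then depend on which page the site followed. The Amendment 12 overview reports that primary completion has passed, so a correction can reach only patients still on treatment. Amendment 12 nevertheless keeps both passages in force and anticipates that patients may remain on treatment.

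**Working it through.** The plan gives no figure to reproduce, and no sample size, power or alpha calculation is involved. The check sets the passages side by side and traces the dose levels.

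**Inputs**

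- Dose levels (Table 6-3): 60, 45 and 30 mg, so at most two reductions from the starting dose.
- Re-escalation after NIP: not allowed (Section 6.4.1; Table 6-7, footnote a).
- Stopping point A (Section 5.2.1.1): Grade 2 NIP that recurs.
- Stopping point B (Table 6-7): the row worded "Grade 2 second re-occurrence".

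**Counting episodes**

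| Grade 2 episode | Section 5.2.1.1 | Table 6-7, literal | Table 6-7, read as second occurrence |
|---|---|---|---|
| 1 (occurrence) | no withdrawal | interrupt, reduce, re-treat | interrupt, reduce, re-treat |
| 2 (first re-occurrence) | withdraw | no row of its own; the plain Grade 2 row can be applied again | discontinue |
| 3 (second re-occurrence) | not reached | discontinue | not reached |

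On the literal reading the passages part at episode 2. On the looser reading they agree.

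**Tracing the dose, first episode at 60 mg**

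- Section 5.2.1.1: 60 → 45, withdrawn at episode 2. Re-treatments: 1.
- Table 6-7, literal, with the plain Grade 2 row applied twice: 60 → 45 → 30, stopped at episode 3. Re-treatments: 2.
- Difference: 3 − 2 = 1 episode, and 2 − 1 = 1 re-treatment.

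The trace restates the two readings in doses. It shows that the literal reading is workable, because there are two levels to step down through. It is not evidence of how often the situation arises.

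**Where the gap may close.** If the second episode occurs at 30 mg, for example after a first episode at 45 mg, footnote a removes the reduction step. The text with the table requires permanent discontinuation when 30 mg is not tolerated. The two passages may then lead to the same outcome.

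**Two smaller differences in the hypertension text**

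- For post-dose hypertension that cannot be managed, the text of Section 6.4.1.2 b) permits a reduction of 1 or 2 levels; the post-dose row of Table 6-8 permits 1.
- For Grade 3 hypertension during infusion, Table 6-8 offers interrupting or slowing the infusion; Section 6.4.2.3 says to interrupt.

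Both are discretionary or recommendation wording, and the main point does not depend on them.

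**The case against.** The strongest reply is that the table's phrase is loose wording for a second occurrence. Read that way, its two Grade 2 rows cover every case without a gap and match Section 5.2.1.1. The Amendment 10 change log supports this: one row introduces the NIP change for both sections and gives a single criterion, Grade 3 or higher or recurrent Grade 2. That makes two deliberately different thresholds unlikely. It is evidence of intent, but a change log is not operative text and does not define the term either.

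A second reply is that the conflict is softer than it looks. Section 6.4.1 lets an investigator choose a more conservative modification with documentation, so withdrawal at episode 2 need not breach either passage. That is fair as far as it goes. But the same section says modifications must follow Sections 6.4.1.1 and 6.4.1.2, and an allowance for discretion is not a statement of which passage takes precedence.

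A third reply is that little in the reported results can move, and this largely stands. SAP Supplement 1.0, Section 6.3.2, reports incidence by worst grade and an exposure-adjusted rate based on time to first occurrence. A second Grade 2 episode changes neither. What could plausibly move are the tabulations by action taken and by outcome, and counts of discontinuation. The documents cited here do not set out a deviation rule for this case, so the effect on deviation counts is a possibility only.

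**Conclusion.** The inconsistency is real and lies in the current text. Read literally, the two passages give different actions for the second Grade 2 NIP episode. The gap is one episode and one re-treatment for a patient whose first episode is at 60 mg, and it may vanish when the second is at 30 mg.

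This rests on two assumptions: that recurrent in Section 5.2.1.1 means the second episode, and that the table's phrase is taken literally. If the phrase means a second occurrence, the rules coincide and only the wording is at fault. The printed text does not settle which applies. The number of patients affected cannot be derived from the documents, and no efficacy endpoint, event count, alpha or power is touched. It should be corrected because it concerns a stopping rule for the one named event of special safety interest. The two passages must be reconciled; this review takes no position on which rule is right.

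**What to change.** The sponsor should decide which rule was intended, state it once by episode number in the format of Tables 6-5 and 6-6, and have the other place cross-refer to it. Table 6-7 should leave no Grade 2 episode without a row. The same edit can align the Section 6.4.1.2 b) text with the post-dose row of Table 6-8, and the during-infusion row of Table 6-8 with Section 6.4.2.3.

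The cost is wording only, in the next amendment or a clarification letter to sites. Data already collected are unaffected.
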